4.2. Exclusion Criteria

Subjects who meet any of the following exclusion criteria will not be eligible for enrollment into the study:

Exclusions related to general health:

- Severe extensive colitis as evidenced by:
 - Physician judgement that the subject is likely to require hospitalization for medical care or surgical intervention of any kind for UC (eg, colectomy) within 12 weeks following randomization
 - Current evidence of fulminant colitis, toxic megacolon or recent history (within last 6 months) of toxic megacolon, or bowel perforation
 - Previous total or partial colectomy
- Diagnosis of CD or indeterminate colitis or the presence or history of a fistula consistent with CD.
- Diagnosis of microscopic colitis, ischemic colitis, or infectious colitis.
- Hospitalization for exacerbation of UC requiring intravenous (IV) steroids within 12 weeks of screening (a single dose of IV steroids given is acceptable).
- 5. Positive assay or stool culture for pathogens (ova and parasite examination, bacteria) or positive test for Clostridioides difficile (formerly known as Clostridium difficile) toxin at screening. (Note: If C. difficile is positive, the subject may be treated and retested
 > 4 weeks after completing treatment.)
- Pregnancy, lactation, or a positive serum β-hCG measured during screening.
- 7. Clinically relevant neurological, endocrine, metabolic (including, but not limited to, hypo- and hyperkalemia), psychiatric, cognitive impairment, alcohol/drug abuse/dependence, or other major systemic disease making implementation of the protocol or interpretation of the study difficult or would put the subject at risk.
- Have any of the following conditions or receiving treatments that may affect cardiovascular function:
 - Myocardial infarction, unstable angina, stroke/transient ischemic attack, decompensated heart failure requiring hospitalization or Class III/IV heart failure ≤ 6 months prior to or during the Screening Period

- History or presence of second-degree or third-degree atrioventricular block, sick sinus syndrome, or periods of asystole for > 3 seconds without a functional pacemaker
- History or presence of recurrent symptomatic bradycardia or recurrent cardiogenic syncope

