- Screening or Week 0/Day 1 prerandomization vital signs (taken in the sitting position) with a heart rate (HR) < 50 beats per minute (bpm) OR systolic blood pressure (BP) < 90 mm Hg OR diastolic BP < 55 mm Hg. Vital signs may be repeated up to 3 times during a visit to confirm abnormal readings
- Screening or Week 0/Day 1 prerandomization electrocardiogram (ECG) with PR interval > 200 ms or Fridericia's corrected QT interval (QTcF) ≥ 450 ms in men or > 470 ms in women
- Start, stop, change or planned change in dosage of any anti-arrhythmic drugs (Class I to IV) ≤ 1 week before screening or within 1 week before or after randomization
- Forced expiratory volume in 1 second (FEV1) or forced vital capacity (FVC) < 70% of predicted values and FEV1/FVC ratio < 0.70 at screening.
- 10. Uncontrolled diabetes as determined by hemoglobin A1c (HbA1c) > 9% at screening, or subjects with diabetes with significant comorbid conditions such as retinopathy.
- History of macular edema or retinopathy.
- 12. History of active tuberculosis (TB), history of untreated or inadequately treated latent TB infection, active or latent TB infection at screening (refer to Appendix 2 for details on TB screening requirements and interpretation of test results). The following are EXCEPTIONS to this exclusion criterion:
 - Subjects with latent TB, who have been ruled out for active TB, have completed an
 appropriate course of TB prophylaxis treatment per national/local medical guidelines
 or WHO guidelines, have a chest radiograph without changes suggestive of active TB
 infection, and have not had recent close contact with a person with active TB are
 eligible to enroll in the study. It is the responsibility of the Investigator to verify the
 adequacy of previous TB treatment and provide appropriate documentation of
 treatment compliance.
 - Subjects diagnosed with latent TB at screening, ruled out for active TB and received
 at least 4 weeks of an appropriate TB prophylaxis regimen may be rescreened for
 enrollment. Subjects will complete their prophylactic regimen during the trial.
- 13. A clinically significant active infection (eg, serious and/or atypical) ≤ 28 days prior to randomization, required IV medication ≤ 14 days prior to randomization, or that may worsen (in the opinion of the Investigator) if the subject is treated with a drug having immunosuppressant effects (ie, etrasimod). Fungal infection of nail beds is allowed.

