9. STUDY ASSESSMENTS AND PROCEDURES

9.1. General Instructions

- Study procedures and their timing are summarized in the Schedule of Assessments (Appendix 1, Table 6). Protocol waivers or exemptions are not allowed.
- Results of all protocol-required procedures will be recorded in the eCRF whenever applicable.
- Immediate safety concerns should be discussed with the Medical Monitor immediately upon occurrence or awareness to determine if the subject should continue or discontinue study treatment.
- Adherence to the study design requirements, including those specified in the Schedule of Assessments (Appendix 1, Table 6), is essential and required for study conduct.
- Study visits should be scheduled in the morning, whenever possible.
- All laboratory assessments required by the protocol will be performed by a central laboratory unless otherwise stated.
- For onsite and offsite study visits (refer to Section 9.6 and Table 6), subjects should take their study treatment after blood draws for PK and after all pre-dose assessments and procedures have been completed.

The Investigator will maintain a screening log and enrollment log to record details of all subjects screened and to confirm eligibility or record reasons for screening failure, as applicable.

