9.3. Screening and Eligibility

Subject eligibility will be assessed based on protocol inclusion and exclusion criteria. All screening evaluations must be completed and reviewed to confirm potential subjects meet all eligibility criteria.

Screening procedures must be completed within 28 days prior to receiving the first dose of study treatment (Appendix 1, Table 6). The Screening Period may be extended for subjects who require additional diagnostic testing/consults to determine status of either latent TB or *C. difficile* infection. If the subject is planned to be randomized > 28 days from the signing of the informed consent form (ICF), the Medical Monitor should be consulted to see if repeated testing is needed. The 28-Day Screening Period may also be extended on a case-by-case basis to accommodate reasonable delays in specific screening assessments (eg, PFTs, OCT) due to testing availability. The Medical Monitor must be consulted prior to extension in each case.

Subjects may have an abnormal laboratory assessment repeated 1 time only. If additional retests are considered, the ability to repeat the laboratory assessment should be discussed with the Medical Monitor and the outcome of the conversation should be documented.

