APPENDIX 2: TUBERCULOSIS SCREENING

All subjects must undergo screening for a history of tuberculosis (TB) infection and testing for latent/active TB infection. Their medical history review must include specific questions about a history of TB or known occupational or other personal exposure to individuals with active TB. Subjects should be asked about past testing for TB, including chest radiograph results and results of interferon-gamma release assay (interferon-gamma release assay [IGRA], eg, QuantiFERON-TB Gold In-Tube, T-SPOT TB) or response to tuberculin skin test (TST) and history of Bacillus Calmette-Guérin vaccination.

- a. Subjects without a history of latent or active TB who have a negative IGRA or TST result at screening are eligible to enroll in the study.
- A TB questionnaire will be completed for all subjects (refer to questionnaire below) during the Screening Period.
- c. For subjects residing in countries with a high burden of TB or multi-drug resistant (MDR) TB as identified by WHO, the TB screening questionnaire will be completed at every study visit (per protocol Schedule of Assessments). For subjects who are receiving TB prophylaxis treatment the TB questionnaire will be completed at every study visit (until TB prophylaxis treatment course is completed). This questionnaire will monitor for any emergent symptoms of active TB and compliance with any TB prophylaxis treatment.
 - For a complete list of TB high burden and MDR TB high burden countries during the period 2021 to 2025, visit:
 - https://www.stoptb.org/securing-quality-tb-care-all/high-burdencountries-tuberculosis
 - https://cdn.who.int/media/docs/default-source/hqtuberculosis/who_globalhbcliststb_2021-2025 backgrounddocument.pdf?sfvrsn=f6b854c2 9
 - https://www.who.int/publications/i/item/9789240037021
- d. The IGRA or TST is NOT required at screening (or annually) for subjects with a history of active/latent TB infection.
 - Subjects with past or current history of active TB, regardless of treatment history, are excluded from enrollment.
 - Subjects with a history of latent TB infection diagnosed prior to screening must have documentation of treatment with at least 4 weeks of an acceptable TB prophylaxis treatment regimen to qualify for enrollment. It is the responsibility of the Investigator to verify the adequacy of previous TB treatment and provide appropriate documentation (Direct Observation Therapy report where available).

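### Appendix 2 item d states a lower TB prophylaxis threshold for latent TB diagnosed before screening than Exclusion 12, and a site using it as a checklist could enrol an excluded subject

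*Protocol*

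**What the plan says.** Exclusion 12 (Protocol Section 4.2, repeated in the synopsis) bars subjects with a history of untreated or inadequately treated latent TB, or with latent TB at screening. It allows two exceptions.

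- Exception 1 covers "Subjects with latent TB, who have been ruled out for active TB, have completed an" appropriate prophylaxis course under national, local or WHO guidelines, with a clear chest radiograph and no recent close contact with active TB.
- Exception 2 covers "Subjects diagnosed with latent TB at screening, ruled out for active TB and received" at least four weeks of prophylaxis. They may be rescreened, and "Subjects will complete their prophylactic regimen during the trial".

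Appendix 2 deals with the same subjects in two items. Item d takes latent TB diagnosed before screening: such subjects "must have documentation of treatment with at least 4 weeks of an acceptable TB prophylaxis treatment regimen to qualify for enrollment", and the investigator must verify and document that earlier treatment was adequate. Item f takes a newly positive test at screening: the subject fails screening, then may be rescreened after starting prophylaxis at least four weeks earlier, with a plan to finish on study. Item g adds an expert assessment of regimen adequacy and treatment duration.

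On which text decides, Section 9.3 says "Subject eligibility will be assessed based on protocol inclusion and exclusion criteria", Section 4.2 opens with "Subjects who meet any of the following exclusion criteria will not be eligible for enrollment into the" study, and Section 9.1 says "Protocol waivers or exemptions are not allowed". Section 9.3.2 sends rescreening after latent TB prophylaxis to Section 4.2. In the other direction, Section 9.3.1 and Table 6 footnote f say that TB screening is done to determine eligibility and point to Appendix 2.

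**The concern.** Item d and exception 1 address the same subjects, and both give the investigator nearly the same duty to verify and document earlier treatment. Where exception 1 asks for a completed course, item d gives only the four-week figure, which Section 4.2 reserves for subjects diagnosed at screening. Item d does not mention a plan to complete either, so it asks less of previously diagnosed subjects than item f asks of newly diagnosed ones.

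The stake is an avoidable eligibility deviation on a safety criterion. Section 1.3 reports a sustained fall in lymphocyte count on etrasimod, and Section 5.1 requires treatment to stop on confirmed active TB. Item d also waives the interferon-gamma release assay or skin test for subjects with a TB history, so documented treatment carries much of the eligibility decision for this group.

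**Working it through.** No arithmetic applies. The check sets the texts side by side, assuming that active TB has been ruled out and that the radiograph and contact conditions of exception 1 are met.

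| Subject | Exclusion 12 | Appendix 2 |
|---|---|---|
| Diagnosed before the first screening for this study, course completed (at least 4 weeks) | Admitted under exception 1 | Item d minimum met |
| Diagnosed before the first screening, at least 4 weeks taken, course unfinished | Excluded | Item d minimum met |
| Diagnosed before the first screening, under 4 weeks taken, course unfinished | Excluded | Item d minimum not met |
| First diagnosed at a screening for this study, at least 4 weeks received, plan to finish on study | May be rescreened under exception 2 | May be rescreened under item f |

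The second row is the problem. Take a subject diagnosed before screening who is five weeks into a longer regimen:

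1. Exception 1 fails because the course is not complete.
2. Exception 2 fails because the diagnosis was not made at screening.
3. With no exception available, Exclusion 12 bars the subject.
4. Item d's stated threshold is met, because five weeks exceeds four and the item does not ask about completion.

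Which text prevails? No sentence says expressly that Section 4.2 overrides Appendix 2, but the documents point that way. Eligibility is assessed on the inclusion and exclusion criteria, meeting any exclusion bars enrolment, waivers are not allowed, and Section 9.3.2 sends prophylaxis rescreens to Section 4.2. Exclusion 12 cites the appendix for a limited purpose: "refer to Appendix 2 for details on TB screening requirements and interpretation of test results". Item d is also phrased as something a subject must have, whereas item a says outright that its subjects are eligible. The strict reading is therefore that the five-week subject is excluded.

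What remains is the practical route to error. Section 9.3.1 and Table 6 footnote f direct sites to Appendix 2 for eligibility, and the only duration stated there for this group is four weeks.

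**The case against.** The strongest reply is that the two texts do not contradict each other. Item d sets a necessary minimum and Exclusion 12 a stricter condition; a subject with a completed course of at least four weeks satisfies both. That is correct. A reader might infer that the protocol makes subjects with unfinished courses eligible, or that it leaves the question open. The documents support neither: item d does not say that meeting its minimum is sufficient, and the provisions on eligibility favour Exclusion 12. What stands against the reply is that a four-week floor adds almost nothing once completion is required, so a site would naturally take it as the working threshold.

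A second reply is that other steps would expose an unfinished course. The investigator must verify adequacy, item g requires an expert to assess regimen and duration, and the Appendix 2 questionnaire, completed for every subject at screening, records start date, expected stop date and missed doses of each prophylaxis drug. This limits the risk but does not remove it: item g states no duration standard, and an assessor looking in Appendix 2 finds only the four-week figure.

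A third reply is that four weeks suits one subject under item d: someone found positive at an earlier screening for this study and rescreened mid-course, whose diagnosis now precedes the current screening. That is a coherent use, but item d's wording is not confined to it.

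Finally, the sponsor might have meant to admit previously diagnosed subjects still on prophylaxis. Widening exception 2 would then be the matching change. Nothing in Section 4.2 or the synopsis indicates that intent.

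**Conclusion.** The point holds as a minor wording defect. For latent TB diagnosed before screening, item d states a lower threshold than the criterion that governs, and a site using Appendix 2 as its checklist could enrol a subject whom Exclusion 12 excludes.

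The conclusion rests on two inferences: that Section 4.2 prevails over Appendix 2, and that exception 1 is the only route for subjects diagnosed before screening. Exception 1 does not name that group; the inference follows from exception 2 being limited to diagnosis at screening.

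The size cannot be expressed in subjects, because the documents give no counts of latent TB or of prophylaxis status. A reader might infer that ineligible subjects have been enrolled; the documents show no such case. Nor is there an effect on the efficacy results to claim. The SAP's Full Analysis Set depends on randomization and dosing, and its Primary Analysis Set adds only baseline disease scores, so neither turns on TB eligibility. No endpoint or power figure changes. Any added safety risk is further limited on study, since Section 9.9.7 repeats the TB questionnaire at each visit until prophylaxis is complete and confirmed active TB stops treatment.

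**What to change.** Amend Appendix 2 item d in two respects:

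- For latent TB diagnosed before the first screening for this study, require a documented, completed, appropriate prophylaxis course, matching exception 1 of Exclusion 12.
- State that subjects first diagnosed at a screening for this study and then rescreened fall under exception 2 and item f: at least four weeks of prophylaxis received, with a plan to complete the course on study. Use received, as exception 2 does, because item f speaks of having initiated the regimen.

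The cost is one wording change carried in a protocol amendment, with the IRB/IEC approval that Sections 11.2 and 11.5 require before implementation. Section 4.2, the synopsis, data collection and the analysis stay as they are.

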			# of Missed Doses:			
	Medicat	ion#2				
			Start date of Medication #2:			
			Expected stop date of Medication #1:			N-
			Have you missed taking any doses of I	Medication #1?	Yes	No
			Dates of Missed Doses:			
			# of Missed Doses:			
	Medicat	ion#3				
			Start date of Medication #3:			
			Expected stop date of Medication #1:			
			Have you missed taking any doses of I	Medication #1?	Yes	No
			Dates of Missed Doses:			
			# of Missed Doses:			

Clinical Study Protocol Phase 2, 52-Week Study in N	foderate UC (GLADIATOR UC)		APD334-210 Amendment 2.1
Medication # 4	_		
	Start date of Medication #4:		
	Expected stop date of Medication #1:		
	Have you missed taking any doses of Med	lication #1?	Yes No
	Dates of Missed Doses:		
	# of Missed Doses:		
Please provide details to	any question answered "Yes."		
Completed by (signatur	e)	Date	

Section 2: To be completed by the investigator

I.	The participant is on concomitant medication(s) with immunosupp If yes, specify medication(s) (name, dosage):	ressive ef	tects: Yes / No				
	Medication #1:						
	Medication #2:						
	Medication #3:						
	Medication #4:						
II.	TB QuantiFERON or Tuberculin Skin Test result: Date:		-				
	Chest x-ray/computer tomography (CT) scan done to rule out pulmonary TB?	Yes	No				
	If yes, date of chest x-ray or CT scan:						
	Any evidence of active pulmonary TB disease on chest x-ray or CT scan?	Yes	No				
	Other assessment completed?	Yes	No				
	If yes, specify assessment:						
	If yes, date of other assessment:						
	Any evidence of active TB disease on assessment?	Yes	No				
Ш.	Upon review of the responses and discussion with the participant, I recommend the following:						
	Perform screening test for latent TB infection						
	Perform additional assessments to rule out active TB disease						
	Refer to physician TB expert for evaluation and treatment						
	Follow up at the next TB-designated study visit and repeat TB screening questionnaire						
T=-	vectigator (cignature)						
In	vestigator (signature) Date						

APPENDIX 3: MAYO CLINIC SCORE - SAMPLE

APPENDIX 4: HISTOLOGICAL SCORING INDICES

Geboes Grading System

The Geboes Grading System is a stepwise grading system used for the evaluation of microscopic inflammation and histopathologic disease activity in ulcerative colitis (UC). The microscopic appearance of the mucosa is categorized into 6 grades. A decrease of the Geboes Score grading system to Grade zero (0) or one (1) indicates mucosal healing (Geboes 2000).

Nancy Histological Index

The Nancy Histological Index is a validated index for assessing histological disease activity in UC. It is composed of 3 histological items defining 5 grades of disease activity: Absence of significant histological disease (Grade 0), chronic inflammatory infiltrate with no acute inflammatory infiltrate (Grade 1), mildly active disease (Grade 2), moderately active disease (Grade 3), and severely active disease (Grade 4). The presence of ulceration on the biopsy specimen corresponds to severely active disease (Grade 4). If there is no ulceration, acute inflammatory cells infiltrate (presence of neutrophils) is assessed. Moderate or severe acute inflammatory cells infiltrate corresponds to moderately active disease (Grade 3), while mild acute inflammatory cells infiltrate correspond to mildly active disease (Grade 2). If there is no acute inflammatory cells infiltrate, assessment of chronic inflammatory infiltrate (lymphocytes and plasmacytes) is made. A biopsy specimen showing moderate or marked chronic inflammatory infiltrate (Grade 1). A biopsy specimen showing mild or no chronic inflammatory infiltrate corresponds to absence of significant histological disease (Grade 0) (Marchal-Bressenot 2017).

Robarts Histopathology Index

[figure not shown]
The Robarts Histopathology Index (RHI) is an evaluative index, derived from the Geboes score, that is designed to be reproducible and responsive to clinically meaningful change in disease activity over time. The total RHI score ranges from 0 (no disease activity) to 33 (severe disease activity) and is calculated as follows: RHI = $1 \times$ chronic inflammatory infiltrate + $2 \times$ lamina propria neutrophils + $3 \times$ neutrophils in epithelium + $5 \times$ erosion or ulceration (Mosli 2017).

APPENDIX 5: GUIDANCE FOR THE ASSESSMENT OF POTENTIAL PROGRESSIVE MULTIFOCAL LEUKOENCEPHALOPATHY

If a subject exhibits signs and symptoms suspicious for progressive multifocal leukoencephalopathy (PML), the Investigator must interrupt study treatment and perform a targeted neurologic examination to assess for signs of PML, which are diverse, progress over days to weeks, and may include progressive weakness on one side of the body or clumsiness of limbs or difficulty with walking or writing or fine motor skills, disturbance of vision, changes in thinking, memory and orientation leading to confusion and (expressive aphasia), and/or agnosia (receptive aphasia). Consultation with a local neurologist may be warranted, as presented in the PML case evaluation algorithm in Figure 2.

The Medical Monitor should be informed of any suspected cases of PML and, if needed, will facilitate Investigator/local neurologist consultation with PML medical experts on the independent adjudication committee.

Figure 2: Progressive Multifocal Leukoencephalopathy Case Evaluation Algorithm

Note: IP dosing may resume, and no further evaluation is needed if the Investigator assessment reveals no objective signs of PML, the local neurologist confirms that the subject does not have PML, or the IAC's review of the evidence concludes that PML is ruled out.

CE, contrast-enhanced; CSF, cerebral spinal fluid; IAC, independent adjudication committee; IP, investigational product; JCV, John Cunningham Virus; MRI, magnetic resonance imaging; PCR, polymerase chain reaction; PML, progressive multifocal leukoencephalopathy; r/o, rule out

